# 1. Statistical Analysis Plan: I8G-MC-LMDC: Assessment of Safety, Tolerability, and Efficacy of LY3303560 in Early Symptomatic Alzheimer's Disease

## Confidential Information

The information contained in this document is confidential and the information contained within it may not be reproduced or otherwise disseminated without the approval of Eli Lilly and Company or its subsidiaries.

**Note to Regulatory Authorities:** This document may contain protected personal data and/or commercially confidential information exempt from public disclosure. Eli Lilly and Company requests consultation regarding release/redaction prior to any public release. In the United States, this document is subject to Freedom of Information Act (FOIA) Exemption 4 and may not be reproduced or otherwise disseminated without the written approval of Eli Lilly and Company or its subsidiaries.

LY3303560

Alzheimer's disease

Multicenter, randomized double-blind, placebo-controlled, Phase 2 study comparing up to 5600 mg of LY3303560 with placebo over 104 weeks in approximately 225 patients with early symptomatic AD.

Eli Lilly and Company  
Indianapolis, Indiana USA 46285  
Protocol I8G-MC-LMDC  
Phase 2

SAP electronically signed and approved by Lilly on date provided below:

### 3. Revision History

SAP Version 1 was approved on Oct. 10, 2018 prior to unblinding. SAP Version 2 was approved on Nov. 19, 2019 prior to efficacy unblinding. SAP version 3 was approved on Aug. 11, 2020 prior to interim analysis 2. SAP version 4 was approved April 21, 2021 prior to interim analysis 3. SAP version 5 was approved August 31, 2021 prior to the primary outcome lock. SAP version 6 was approved prior to the primary outcome lock and included the following changes:

- Fixed typo in description of number of missing items allowed in the ADAS-Cog13 scale (sec. 6.3)
- Added the Bayesian DPM thresholds for the Multiplicity Graph for iADRS LY5600 vs. placebo and iADRS LY1400 vs. placebo and a description calculating all of the thresholds included in the Multiplicity Graph (sec. 6.11.2)
- Updated ECG timepoints (sec. 6.13.6)
- Added two subgroup analyses: baseline tau grouped into thirds and baseline MMSE grouped into thirds, and updated subgroup definitions of disease severity based on MMSE (sec. 6.14)

## 4. Study Objectives

### 4.1. Primary Objective

The primary objective of protocol I8G-MC-LMDC (LMDC) is to test the hypothesis that LY3303560 administered for 100 weeks will decrease the decline in cognitive and/or functional outcomes in patients with early symptomatic Alzheimer's Disease (AD) relative to placebo as measured by the integrated Alzheimer's Disease Rating Scale (iADRS) score from baseline to 104 weeks.

### 4.2. Secondary Objectives

The secondary objectives of LMDC are to assess the effect of LY3303560 versus placebo on clinical progression, on brain aggregated tau deposition, and on attenuating downstream markers of the neurodegenerative process in patients with early symptomatic AD and evaluate the safety and tolerability of LY3303560.

Clinical progression will be assessed by change from baseline to 104 weeks in cognition and/or function as measured by the following:

- Alzheimer's Disease Assessment Scale—Cognitive subscale (ADAS-Cog13) score
- Alzheimer's Disease Cooperative Study—instrumental Activities of Daily Living scale (ADCS-iADL) score
- Clinical Dementia Rating Scale – Sum of Boxes (CDR-SB) score
- Mini-Mental State Examination (MMSE) score

Brain aggregated tau deposition will be assessed by change from baseline through 104 weeks as measured by flortaucipir F 18 PET scan.

Attenuation of downstream markers of the neurodegenerative process in AD will be assessed by change from baseline through 104 weeks as measured by volumetric magnetic resonance imaging (vMRI).

Safety assessments used to evaluate the safety and tolerability of LY3303560 include the following:

- Spontaneously reported adverse events
- Clinical laboratory tests
- Vital signs and body weight measurements
- 12-lead ECGs
- Physical and neurological exams
- Anti-drug antibodies
- Safety MRIs

- Columbia Suicide Severity Rating Scale (C-SSRS)

### 4.3. Exploratory Objectives

The exploratory objectives described in the protocol for study LMDC are in the following table:

Exploratory Objectives	Exploratory Endpoints
To assess the effect of LY3303560 versus placebo on clinical progression in patients with early symptomatic AD.	Change in dependence level derived from ADCS-ADL scale scores from baseline to 104 weeks.
To assess the effect of LY3303560 versus placebo on clinical progression in patients with early symptomatic AD.	Change in cognition from baseline to 104 weeks as measured by the change in: 
 
• CogState Brief Battery (CBB)
 

To assess peripheral PK and presence of anti-LY3303560 antibodies over 104 weeks.	
 
• Maximum serum concentration of LY3303560 at steady state (<math>C_{max,ss}</math>).
 
• Anti-drug antibodies (ADA) against LY3303560 including treatment-emergent ADA and neutralizing antibodies.
 

To assess the effect of LY3303560 versus placebo on clinical progression as measured by Digital Clock Drawing test (DCTClock) in patients with early symptomatic AD.	Change in DCTClock results from baseline through 104 weeks.
To assess the initial effect of LY3303560 versus placebo on plasma total tau and phospho181tau concentrations in patients with early symptomatic AD.	Change from baseline to steady state (16 weeks) in plasma tau and phospho181tau levels.
To assess the steady state effects of LY3303560 versus placebo on plasma tau and phospho181tau concentrations in patients with early symptomatic AD.	Change in plasma tau and phospho181tau concentrations at steady state through 104 weeks.
To assess the utility of DCTClock and plasma phospho181tau in screening phase efficiency for trials of patients with early symptomatic AD.	Associations of DCTClock and plasma phospho181tau with MMSE, CBB, screen failure categories, and baseline data from enrolled subjects.

Additional exploratory objectives not included in the protocol are described in the following table:

To assess the initial effect of LY3303560 versus placebo on plasma ptau217 and Neurofilament light chain (NfL) concentrations in patients with early symptomatic AD.	Change from baseline to steady state (16 weeks) in plasma ptau217 and NfL.
To assess the steady state effects of LY3303560 versus placebo on ptau217 and NfL concentrations in patients with early symptomatic AD.	Change in ptau217 and NfL at steady state through 104 weeks.

## 5. Study Design

### 5.1. Summary of Study Design

Study LMDC is a multicenter, randomized, double-blind, placebo-controlled, Phase 2 study of LY3303560 in patients with early symptomatic AD and low-to-medium cerebral tau burden. A combination of visual and quantitative assessments of tau PET is used to identify eligible patients:

- Visual assessment of AD+ (increased activity in posterior temporal regions only) AND  $1.10 < \text{SUVR} \leq 1.46$
- Visual assessment of AD++ (increased activity in temporal and parietal regions) AND  $\text{SUVR} \leq 1.46$

The maximum possible duration of the study is 121 weeks that includes a screening period of up to 8 weeks, a treatment period of 100 weeks, a 4-week post last dose assessment, and an immunogenicity and safety follow-up period of up to 13 weeks, following the last dose of the study drug at Week 100. Subjects who meet entry criteria will be randomized in a 1:1:1 ratio to one of the following treatments:

- **1400 mg LY3303560:** LY3303560 1400 mg IV infusion Q4W for 100 weeks (Visit 2 [Week 0] to Visit 27 [Week 100]).
- **5600 mg LY3303560:** LY3303560 5600 mg IV infusion Q4W for 100 weeks (Visit 2 [Week 0] to Visit 27 [Week 100]).
- **Placebo:** IV placebo infusion Q4W for 100 weeks (Visit 2 [Week 0] to Visit 27 [Week 100]).

The first safety review by a Data Monitoring Committee will be conducted after approximately 30 patients have received 3 doses and completed the 4 week assessment period ( i.e. just prior to their 4th dose). Enrolment will halt after these patients have received one dose of study treatment, however those patients already dosed will continue their allocated treatment. If any of these patients discontinue from study treatment for reasons other than safety, they may be replaced, upon discussion between the investigators and Lilly.

The primary hypothesis being tested is that LY3303560 administered for 100 weeks will result in a significant slowing in cognitive/functional decline compared with placebo as measured by the change from baseline to the end of the double-blind period (Week 104) on the integrated Alzheimer's Disease Rating Scale (iADRS), in subjects with early symptomatic AD (where early symptomatic AD refers to the combination of 2 stages: prodromal AD [mild cognitive impairment (MCI)-AD] and mild dementia due to AD; Alaka et al. 2015) who have low-to-medium tau burden.

### 5.2. Determination of Sample Size

Based on the Disease Progression Model (DPM), 360 enrolled patients, a 30% dropout rate, and a 3-month delay of treatment effect onset, this sample size will provide more than 95% power to

demonstrate that at least one of the active treatment arms has slowed cognitive/functional decline. This claim of slowing cognitive/functional decline is based on showing that at least one of the active treatment arms has a  $\geq 0.6$  posterior probability of slowing of iADRS progression over placebo by at least 4 points (that is, 25% slowing relative to placebo, based on a mean change from baseline in the placebo group of 16 points and mean change from baseline on at least one of the active treatment arms of at most 12 points) after 104 weeks (approximately 24 months) on study treatment. This power calculation comes from simulations using a placebo decline of 19.56 points and 33% slowing on 1400 mg LY3303560 and 50% slowing on 5600 mg LY3303560 relative to placebo at 104 weeks. The variance-covariance matrix in the simulations had a variance at Week 104 of 436.85 (equal to a standard deviation of 20.9). If both active treatment arms are placebo-like with no efficacy, the probability of passing the efficacy criterion specified above (that is, false positive) is approximately 2.5%. To test the hypothesis of a disease progression benefit, we calculate the posterior probability of superiority in cognitive/functional slowing, and if it is above a pre-specified threshold (which controls the experiment-wise type I error at approximately 2.5%), then a claim of cognitive slowing will be made. The simulation for the power calculation and sample size determination was carried out in FACTS Version 5.5.

### 5.3. Method of Assignment to Treatment

Patients who meet all criteria for enrollment will be assigned a study (patient) number at Visit 1 and randomized to double-blind treatment at Visit 2. Patients will be randomized to LY3303560 or Placebo in a 1:1:1 ratio. Assignment to treatment groups will be determined by a computer-generated random sequence using an interactive web response system (IWRS). For the first, approximately, 30 patients, the IWRS will be programmed to guarantee balance between the arms for the first interim analysis for safety; this is referred to as the burn-in period. After the burn-in period, patient randomization will then follow the dynamic allocation (minimization) method of Pocock and Simon (1975) to balance the treatment arms using investigative site as a factor. This is to ensure balanced patient assignment between treatment arms within each site at the end of the study.

### 5.4. Interim Analyses

An external DMC is authorized to evaluate results from unblinded interim analyses for the assessment of safety, to recommend any modifications to the study (such as stopping the study or dropping an arm), and to assess efficacy to inform future development. Operational details and any efficacy decision rules will be provided in the DMC charter and the interim efficacy SAP. Study sites will receive information about interim results ONLY if relevant for the safety of their patients. Unblinding details will be specified in the separate unblinding plan document.

The first unblinded DMC review for safety will be conducted once approximately 30 patients have completed 3 months of exposure to study treatment (i.e., after completing 4 weeks following the third dose of study treatment). No patients beyond this initial group of approximately 30 patients will be dosed until the DMC review has been completed and the recommendation is to continue the study. This initial group will continue treatment during the assessment period.

The purpose of the second interim analysis is to evaluate efficacy results from unblinded interim analyses to inform future development, as well as to evaluate safety. This second unblinded DMC review will be conducted after approximately all patients have had the opportunity to complete 12 months of exposure to study treatment (i.e., 4 weeks after the 12th dose at Visit 15 [Week 52]). Treatment will continue during the second interim analysis. With regard to safety, the outcomes of the DMC reviews could be to: 1) continue as planned, 2) modify the protocol, including additional interim analyses, and 3) stop the study. The outcomes with regard to efficacy will be detailed in the interim efficacy SAP.

The purpose of the third interim analysis is to evaluate safety. This third unblinded DMC review will be conducted after approximately all patients have had the opportunity to complete 18 months of exposure to study treatment (i.e., 4 weeks after the 18th dose at Visit 22 [Week 80]). Treatment will continue during the third interim analysis. With regard to safety, the outcomes of the DMC reviews could be to: 1) continue as planned 2) modify the protocol, including additional interim analyses and 3) stop the study

To facilitate PK/PD interim analyses and to initiate the final population PK/PD model development processes, a limited number of preidentified individuals may also gain access to the unblinded data, as specified in the unblinding plan. This will be conducted at the same time as the second DMC. In preparation for the final analysis, access may also be granted after all patients complete 88 weeks of treatment (i.e., Visit 24). Information that may unblind the study during the analyses will not be reported to study sites or blinded study team until the study has been unblinded.

Quarterly, blinded trial level safety reviews will be carried out as documented in the trial level safety review plan.

## 6. A Priori Statistical Methods

### 6.1. General Considerations

The protocol calls for a Data Monitoring Committee (DMC) charged with making decisions regarding patient safety and interim efficacy. This analysis plan describes analyses for the final clinical study report and all interim safety analyses for the DMC.

All analyses will follow the intention-to-treat (ITT) principle unless otherwise specified. An ITT analysis is an analysis of data by the groups to which subjects are assigned by random allocation, even if the subject does not take the assigned treatment, does not receive the correct treatment, or otherwise does not follow the protocol. Consistent with ITT studies the estimand for Study LMDC is the Treatment Policy estimand. Safety analyses will group subjects based on the actual treatment received. If a patient receives a treatment different than the randomized treatment for the duration of the placebo-controlled period, then that different treatment is the actual treatment; otherwise, the actual treatment is the planned treatment.

Unless otherwise noted, all pairwise tests of treatment effects will be conducted at a 2-sided alpha level of 0.05; 2-sided confidence intervals (CIs) will be displayed with a 95% confidence level. All tests of interactions between treatment and other factors will be conducted at an alpha level of 0.05.

Unless otherwise noted no formal statistical hypothesis testing will be made during the first safety interim. Any reported p-values that may be reported as part of standardized output are merely for information purposes only.

Unless otherwise noted baseline is defined as the last measurement prior to dosing. When change from baseline is assessed, subjects will only contribute to the analysis if both a baseline and a post-baseline measurement are available. Endpoint is the last non-missing post-baseline measurement within the time period for the given analysis. For mixed-effect model for repeated measures (MMRM) models, observations collected at nonscheduled visits will not be included in the analyses (Andersen and Millen 2013). For analyses using last observation carried forward (LOCF), the last nonmissing post-baseline observation (scheduled or unscheduled) will be used to calculate change from baseline.

Any change to the data analysis methods described in the protocol will require an amendment ONLY if it changes a principal feature of the protocol. Any other change to the data analysis methods described in the protocol and the justification for making the change will be described within this SAP and clinical study report. Additional exploratory analyses of the data will be conducted as deemed appropriate.

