## 6.3. Handling of Dropouts or Missing Data

### 6.3.1. *Handling Missing Data from Patient Dropouts*

A likelihood-based mixed effects model for repeated measures will be used to handle missing data. The model parameters are simultaneously estimated using restricted likelihood estimation incorporating all of the observed data. Estimates have been shown to be unbiased when the missing data are missing at random and when there is ignorable non-random missing data.

Repeated measures and disease progression model analyses will only use data from visits where the data was scheduled to be collected (Andersen and Millen 2013). When patients discontinue from the study early, there may be efficacy or safety data measurements at visits where the variables were not scheduled to be collected. This data will be used in all other analyses.

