## 6.11. Efficacy Analyses

### 6.11.1. Primary Outcome and Methodology

The primary objective of this study is to test the hypothesis that IV infusion of LY3303560 will slow the cognitive and/or functional decline of AD as measured by the composite measure iADRS compared with placebo in patients with early symptomatic AD. This will be assessed using a Disease Progression Model (DPM).

The iADRS at each scheduled visit (according to the SoA) during the treatment period will be the dependent variable. The DPM is as follows:

$$Y_{ij} = \gamma_i + e^{\theta T_i} \sum_{v=0}^j \alpha_v + \mathbf{x}'_i \boldsymbol{\beta} + \varepsilon_{ij}, i = 1, 2, \dots, k; j = 1, 2, \dots, l$$

where  $Y_{ij}$  denotes the clinical outcome at visit  $j$  for participant  $i$  and clinical outcome score at baseline (prior to treatment) is  $Y_{i0}$ .  $\gamma_i$  ( $i=1, 2, \dots, k$ ) represents the random participant effects.  $T_i$  denotes the treatment arm for participant  $i$ .  $T_i$  takes a value of 1 if a participant is randomized to the low dose, a value of 2 for high dose, and a value of 0 for placebo.  $e^{\theta T}$  is the disease progression ratio (DPR) for treatment  $T$  and  $e^{\theta T} = 1$  for placebo.  $e^{\theta 1}$  and  $e^{\theta 2}$  represent the DPR of the low dose and the high dose, respectively. Furthermore,  $\alpha_v$  is the change in mean cognitive score for placebo from visit  $v-1$  to  $v$ .  $\varepsilon_{ij}$  is the error term. Additional covariates  $\mathbf{x}_i$  will include pooled site ID, age, and baseline AChEI/memantine use (yes/no).

The DPM model assumes the treatment effect of LY3303560 is proportional to placebo over the course of the study. This proportionality assumption is similar to the assumption made in proportional hazards modeling of time to event data. The DPM includes generally diffuse priors on all parameters. The precision value for the prior distribution of all parameters is set to a small value; therefore, the prior distributions on all parameters have very little impact on the posterior distributions. No information or knowledge of the effect of LY3303560 from previous studies will be incorporated into the prior distributions, and the inference will be based on Study LMDC only. Diffuse priors will be used.

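### The SAP declares a treatment policy estimand, but the primary DPM credits active-arm patients who have no data after leaving the study with their arm's full slowing to Week 104

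*SAP*

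**What the plan says.** Section 6.1 commits the trial to intention-to-treat and adds: "Consistent with ITT studies the estimand for Study LMDC is the Treatment Policy estimand". It keeps patients in their randomized group even if they do not take the assigned treatment.

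Section 6.11.1 defines the primary analysis. Each active arm has a single disease progression ratio (DPR), constant over visits, with a random participant effect and covariates. It states: "The DPM model assumes the treatment effect of LY3303560 is proportional to placebo over the course of the study". Nothing in the model depends on stopping drug or leaving the study.

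Section 6.3.1 handles dropout by a likelihood-based repeated-measures model and claims: "Estimates have been shown to be unbiased when the missing data are missing at random and when there is ignorable non-random missing data". It limits both the repeated-measures and DPM analyses to visits at which the scale was scheduled.

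Section 6.11.3.4 plans an exploratory tipping-point analysis in which active-arm discontinuers are assumed to do worse than missing at random (MAR) implies. A delta that starts at 0 and rises in steps of 0.10 is added to their imputed iADRS values.

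Section 5.2 plans for "360 enrolled patients, a 30% dropout rate, and a 3-month delay of treatment effect onset".

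**The concern.** A treatment policy estimand asks what happens to everyone assigned to an arm, including those who leave. A patient who leaves receives no more infusions. If no scores are collected afterwards, the DPM has only that patient's earlier visits and the arm's common ratio. Fitted to observed data without a model for missingness, it treats the unseen course as following the arm's ratio to Week 104. For these patients that is an effect as if they had stayed. It equals the policy effect only if slowing continues to accrue after withdrawal, which the SAP neither states nor justifies.

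No other analysis in 6.11.3 fills the gap. The MMRM, spline, slope and permutation analyses rest on similar likelihood models. The completer and per-protocol analyses move further from treatment policy. The tipping-point analysis looks for the shift that overturns significance and does not estimate a policy DPR.

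At stake is the label on the main result: a percentage slowing would be reported as treatment policy while it answers a more favourable question for part of the sample.

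**Working it through.** **Inputs from section 5.2.** 360 patients; placebo decline 19.56 points; slowing 33% (1400 mg) and 50% (5600 mg); dropout d = 0.30; onset delay 3 months of 24, or 0.125 of follow-up; SD 20.9 at Week 104. Section 5.3: "Patients will be randomized to LY3303560 or Placebo in a 1:1:1 ratio", so 360/3 = 120 per arm, and 120 × 0.70 = 84 with Week 104 data.

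**The plan's own figure.** Section 5.2 claims more than 95% power that at least one active arm meets a "posterior probability of slowing of iADRS progression over placebo by at least 4 points" of at least 0.6. The section equates that margin with 25% slowing. In a Monte Carlo check on Week 104 means, an arm passes if (0.75 × placebo decline − active decline)/SE exceeds the normal quantile at 0.6, with a shared placebo arm. Power is 95.2% with 84 per arm and 97.6% with 120. An approximate DPM with 8 assumed visits and three assumed covariances gives 96.7% to 99.1%. The stated power is reproduced. The SAP title block says approximately 225 patients; the percentages below do not depend on the sample size.

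**Policy effect relative to the DPM effect.** Let r be the mean share of the Week 104 benefit that a patient without later data keeps. Then

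g = (1 − d) + d × r, and overstatement relative to the policy effect = 1/g − 1.

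Assumptions, none given in the SAP: all 30% have no later data; accrued benefit is kept; decline then runs at the placebo rate; benefit accrues linearly. r is then the mean dropout time t as a fraction of 104 weeks. With the delay, it is the mean of max(0, (t − 0.125)/0.875).

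**Base case, uniform dropout.** r = 0.50, so g = 0.70 + 0.30 × 0.50 = 0.85 and 1/0.85 − 1 = 17.6%.
- 33% slowing: 0.33 × 19.56 = 6.45 points; × 0.85 = 5.49. The DPR moves from 0.67 to 1 − 0.33 × 0.85 = 0.72.
- 50% slowing: 0.50 × 19.56 = 9.78 points; × 0.85 = 8.31. The DPR moves from 0.50 to 0.575.

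With the 3-month delay, r = 0.4375, g = 0.831 and the overstatement is 20.3%.

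| Dropout timing | r, no delay | g, no delay | Overstatement, no delay | Overstatement, 3-month delay |
|---|---|---|---|---|
| Uniform, weeks 52–104 | 0.75 | 0.925 | 8.1% | 9.4% |
| Back-loaded (triangular) | 0.667 | 0.900 | 11.1% | 12.9% |
| Uniform, weeks 0–104 | 0.50 | 0.850 | 17.6% | 20.3% |
| Constant hazard | 0.470 | 0.841 | 18.9% | 21.7% |
| Front-loaded (triangular) | 0.333 | 0.800 | 25.0% | 28.8% |
| Uniform, weeks 0–52 | 0.25 | 0.775 | 29.0% | 33.7% |

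**Bounds at 30%.** Slowing continues in full after withdrawal: g = 1, 0%. Benefit lost entirely: g = 0.70, 1/0.70 − 1 = 43%.

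**Less missing data.** Uniform timing, no delay: 10% missing gives 1/0.95 − 1 = 5.3%; 20% gives 1/0.90 − 1 = 11.1%.

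**Effect on the decision.** Section 6.11.2 requires Pr(DPR < 0.75) above 0.51 for 5600 mg and above 0.99928 for 1400 mg. A Week 104 approximation puts this probability at Φ[(0.75 − DPR) × 19.56/SE], with SE = 20.9 × √((1 + 0.75²)/n): 2.85 at n = 84 and 2.38 at n = 120.
- 1400 mg: about 0.71–0.74 at DPR 0.67 and 0.58–0.60 at 0.72. Both miss 0.99928.
- 5600 mg: about 0.96–0.98 at DPR 0.50 and 0.88–0.92 at 0.575. Both exceed 0.51.

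**Delta sign.** Section 6.3.2 defines iADRS as 85 minus ADAS-Cog13 plus ADCS-iADL, so higher is better. Adding a delta that rises from 0 improves the imputed active-arm scores, the opposite of what 6.11.3.4 sets out to do.

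**The case against.** The strongest objection is that stopping drug is not the same as leaving the study. Section 6.1 analyses patients as randomized, section 6.11.3.7 separates remaining in the study from remaining on treatment, and nothing removes scheduled off-drug scores from the primary DPM. Those scores pull the arm's ratio toward the policy effect. This stands. A reader might infer that every withdrawn active-arm patient is credited with full slowing; the SAP supports that only for patients with no scheduled data after leaving. How many there will be depends on follow-up rules that may sit in the protocol, which was not available.

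Second, the size rests on assumptions. The SAP gives no dropout timing and no course after withdrawal, and does not say whether 33% and 50% are on-treatment or net effects. This also stands. A reader might settle on a fixed 10–20%. As a share of the reported effect, 10%, 15% and 20% are the shortfalls at g = 0.90, 0.85 and 0.80; relative to the policy effect they are 11%, 18% and 25%, and other timings fall outside that band.

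Third, a missing-not-at-random analysis is already planned. That is a partial answer: it is exploratory, has no stated link to the DPM, yields no policy estimate, and has the wrong sign as written.

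Fourth, the unbiasedness sentence in 6.3.1 describes the restricted-likelihood repeated-measures model, not the Bayesian DPM. That is correct, so it is a wording error and not evidence about the primary model. It is still wrong, since under the usual definitions non-random missingness is not ignorable.

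**Conclusion.** The mismatch is real but limited. For active-arm patients without scheduled data after leaving the study, the primary DPM assumes continued proportional benefit, and section 6.1 labels the result treatment policy. In the uniform base case the reported effect is about 18% larger than the policy effect, or about 20% with the plan's onset delay. Across the timings examined the range is about 8% to 34%, with bounds of 0% and 43%. If only 10–20% of patients have missing data, the uniform case gives about 5% to 11%. Any bias of this kind favours the active arms.

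Two stronger conclusions are tempting and not supported. A reader might infer that the 1400 mg decision is at risk because a DPR of 0.72 lies close to 0.75. The 0.99928 cutoff is far from being met at either 0.67 or 0.72, and 5600 mg passes at either 0.50 or 0.575, so at the planned effects neither decision changes. A reader might also infer an inflated false-positive rate. With no drug effect there is no benefit to extrapolate, so this mechanism does not inflate it. The issue is the size and meaning of the reported slowing.

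**What to change.** 1. In 6.1 and 6.11.1, state that for patients with no data after study withdrawal the DPM assumes continued proportional benefit under MAR, and that scheduled off-drug scores are included.
2. Add one prespecified supplementary iADRS analysis. Impute active-arm scores after study withdrawal with placebo increments from the point of withdrawal (copy increments in reference). Keep MAR for placebo and for intermittent gaps. Refit the DPM to each imputed dataset and pool the posterior draws. Report its DPR and Week 104 difference beside the primary. Set no new success threshold: the cutoffs in 6.11.2 are calibrated for the existing DPM, and the primary test stays as it is. Placebo-rate decline is itself an unverifiable assumption and should be labelled as one.
3. In 6.11.3.4, correct the sign so that delta lowers imputed iADRS scores.
4. In 6.3.1, delete the claim of unbiasedness for ignorable non-random missing data.

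The cost is SAP wording and extra model fits, with no new data. The supplementary figure will probably be less favourable than the primary DPR. The change counts as prespecified only if made before efficacy unblinding; if made later, the analysis should be labelled post hoc.
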